8.8. Compensation

- **Participants will be compensated up to \$60 dollars once they have completed their 6 month visit for completing the study. The compensation will be in the form of a gift card. Study staff may either provide the gift card in clinic or mail the gift card (s) to participants. A form will be included with the mailed gift card for the participant to sign, confirming the participant received the gift cards. Instructions will be provided to the participant to sign and return the form back to staff via a pre-paid envelope.**

9 CRITERIA FOR EVALUATION OF ENDPOINTS

9.1 Physical Function Performance

The primary endpoint associated with the evaluation of improvement in mobility performance is the result of the 6MW test (6MW distance). The distance patients can walk indoors on a 25

to 30 meter level smooth-surfaced track over the course of 6 minutes will be measured at baseline as well as at the time of discharge and at the 2 and 6 months follow-up. Efforts will be made to ensure consistent 6MW testing conditions throughout data collection for each participant. Median distances will be computed for each arm at the various time points and the expected post-surgery decline and recovery during follow-up will be compared between arms. To accommodate policy and concerns surrounding the COVID-19 pandemic, the current 6MW test track of 25 meters may need to change on occasion and relocate from Clinic 1A to areas with walking tracks that range between 25-30 meters. Because all other operating procedures surrounding the 6MW test will remain identical we do not expect any issues related to the fidelity of the test.

A secondary endpoint associated with the evaluation of improvement in physical performance is the result of the short physical performance battery test. The SPPB score (ranging from 1 to 12) will be obtained for each patient at the time points described above. Medians will be obtained and compared for each arm.

9.2 Patient Reported Outcomes

Questionnaires aimed at measuring disease specific symptoms, multidimensional fatigue, common mental health issues (i.e., depression, anxiety, and alcohol use), and hypothesized treatment mechanisms will be obtained on this study at baseline, at discharge, and at the 2 and 6 months follow-up. The effect of the PEP intervention on patient reported outcomes will be evaluated by comparison between each arm of the study.

9.3 Exploratory Objectives

Data gathered from all patients who received the PEP intervention and pertaining to the quality of the intervention, participation in the intervention, and attitudes toward exercise (obtained via questionnaires) will be analyzed.

Additionally, the effects of the PEP intervention on the following will be evaluated by comparison between each arm of the study:

- Rate of complications (pulmonary and cardiac events, other complications requiring treatment [e.g., liver dysfunction, gastric ulcer, wound infection, colitis, depression], readmissions, and deaths within the first 30 days after discharge).
- Length of stay post-surgical intervention.
- Death and/or hospitalization post-study relating to COVID-19.

Finally, the effects of the PEP intervention on the following will be evaluated by comparison between each arm of the study:

- Total cost of care and utilization (obtained through the UUHS VDO, the Utah APCD, the health care utilization questionnaires, the financial strain (COST) questionnaire and time-line follow-back).
- Levels of potential prognostic or mechanistic biomarkers such as inflammatory biomarkers, in serum, plasma, and buffy coat. Additionally, smoking status post-surgery and microbiome will be assessed.

- Assess the impact of the Coronavirus (COVID-19) on the study and its participants during the outbreak. A limited dataset (including first name, email address, zip code and study ID) may be shared with IRB_00140849 'Exemption Umbrella Protocol- HCI projects to facilitate a larger review of the impact of COVID-19 on all patient populations listed in the umbrella protocol.

Additional Exploratory Objectives:

- Comparison of paired 6 minute walk tests completed by the same patients in clinic and remotely. Prediction of in clinic 6 minute walk test from remote 6 minute walk test of the same patient.
- Prediction of missing 6MW from completed 6MW and other covariates.

The following information will be abstracted from each participant's medical record to allow the UUHS VDO and Utah APCD staff to provide information on the total cost of care and utilization. It has been required by the UUHS VDO staff that the protocol outlines the specific medical record information before they will provide their services. However, any additional medical record information not already outlined below may also be used by study staff.

- Demographics:
 - Age at time of first clinic visit
 - Date of birth
 - Gender
 - Body Mass Index
 - weight
 - Patient's Zip Code (to help with calculation of distance to Huntsman)
 - Race: Caucasian, Black, Hispanic, Asian, Native American, Other
 - Zubrod Performance Scale
 - 0 = Normal activity, no symptoms
 - 1 = Symptoms but fully ambulatory
 - 2 = Symptoms but in bed less than 50% of the time
 - 3 = Symptoms but in bed >50% but less than 100%
 - 4 = Bedridden
 - 5 = Moribund
- Risk Factors for complications (Yes/No answers)
 - Weight loss in past 3 months greater than 3 kgs (captured in questionnaire)
 - Infection at the time of initial clinic visit (e.g., pneumonia)
 - Co-morbidities
 - Hypertension
 - Steroid use
 - Congestive Heart Failure

- Coronary Artery Disease
 - Peripheral Vascular Disease
 - Preoperative Chemotherapy
 - Preoperative Radiation therapy
 - Prior Cardiothoracic Surgery
 - History of Stroke
 - Diabetes
 - Renal insufficiency history (documented history of renal failure and/or a history of creatinine value > 2.0)
 - Other co-morbidity not listed above
- Tobacco Use
 - Use of smokeless tobacco
 - Cigarette use
 - Pack Years (no. of packs per day x no. of years smoking)
 - Tobacco Pipe
 - Tobacco Other
- Status of Tobacco Use History
 - Never Smoker
 - Active smoker at time of clinic visit (this patient will be classified for our paper eventually as a recent quitter, as we have a policy of not operating on those who continue to smoke)
 - Quit smoking >12 months before surgery (remote smoker)
- Pulmonary Function Tests
 - Forced Expiratory Volume in 1 second (FEV1): Value and % predicted
 - Diffusion Capacity (DLCO): Value and % predicted
- Outcomes
 - Procedure Type (VATS [either traditional or robot] OR Thoracotomy)
 - Amount of Lung Resection (Wedge Resection, Segmentectomy, Lobectomy, OR Pneumonectomy)
 - Inpatient AMPAC Score at time of discharge
 - Complications postoperatively
 - Pneumonia
 - Air Leak greater than 5 days
 - Adult Respiratory Distress Syndrome (ARDS)
 - Pulmonary Embolus
 - Initial ventilator support >48 hours in the postoperative period
 - Reintubation
 - Tracheostomy
 - Cardiac arrhythmias
 - Bleeding
 - Neurological Event
 - Renal Event
 - Chylothorax

- Wound Infection
 - Other Infection
 - Length of Inpatient Stay
 - Lung Cancer Pathology Description
 - Primary or Secondary
 - If Primary, Lung Cancer Stage
 - Discharge Date
 - Discharge Location (Home, Skilled Nursing Facility, Rehab facility)
 - Readmission within first 30 days after discharge (to Hospital)
 - Additional Therapy after Surgery
 - Postoperative Chemotherapy
 - Postoperative Radiation Therapy
 - Clinic Visits After Discharge
 - Routine (1-2 weeks, 2 months, 6 months)
 - Additional clinic visits to routine
- Financial/Cost
 - type of insurance
 - -service start/end date
 - -weight
 - -inpatient/er visit indicator
 - -outpatient/office visit indicator
 - -physical therapy indicator
 - -home nursing visit
 - -skilled nursing facility/rehabilitation hospital
 - -charge amount
 - -ICD-9/10 diagnosis codes
 - -ICD-9/10 procedure codes
 - -CPT codes

10 STATISTICAL CONSIDERATIONS

10.1 Randomization

Randomization will have a uniform 1:1 allocation ratio with block sizes of 8. The random allocation sequence will be stratified by the mobility staging (high vs. low) provided by the pre-treatment AM-PAC stage and whether it is a primary or secondary lung cancer diagnosis, based on primary data (as described in section 2.4), the AMPAC stage is sufficient to assess physical function.

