3.3 Number of Study Centers

This study will open at a single center at the Huntsman Cancer Institute. Study procedures may be performed at the Huntsman Cancer Hospital, the University of Utah Farmington clinic, or remotely. The remote option will only be used in circumstances when staff is not able to perform study procedures on site. Staff will take necessary steps to ensure participant safety and confidentiality at all times when performing procedures remotely.

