4.2 Exclusion Criteria

Yes/No (Response of "yes" = patient ineligible)

- 4.2.1 _____ Deemed ineligible for surgery by the enrolling physician
- 4.2.2 _____ Abnormalities on screening physical exam judged by study physicians or supervising physical therapist to contraindicate participation in exercise program compliance.
- 4.2.3 _____ Alcohol or drug abuse as judged by study physicians.
- 4.2.4 _____ Significant mental or emotional problems that would interfere with study participation, or as assessed by the NCCN Distress Thermometer. Any value higher than 7 on the NCCN Distress Thermometer will trigger further assessment, but ultimately enrollment into the clinical trial will be determined by the enrolling physician.

I certify that this patient meets all inclusion and exclusion criteria for enrollment onto this study.

Investigator Signature

Date

Time

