8 STUDY PROCEDURES

8.1 Pre-Surgery Clinic Visit

During their pre-surgery clinic visit (which typically takes place 2-4 weeks prior to surgery as long as surgery is not delayed), all potential lung cancer patients who are surgical candidates (as determined and approved by the surgeon) will be approached about the PEP study. Enrollment may be postponed, and the decision to do so is dependent on all three principal investigators' discretion. This visit may be completed 1 week or up to 6 months prior to surgery depending on the health of the patient and surgical policies. This window may increase if patient and surgical policies require it. Patients who are interested and potentially eligible will undergo the following procedures either in the clinic space or at the Population Sciences (HOPE) clinic located in HCI Research North. All procedures listed below can, as is practical and applicable, also be performed by the study team and participants via telephone, text, email, snail mail, and/or MyChart:

- Informed consent. Consenting may be performed remotely, via phone, video chat, mail and/or email in situations where study staff is unable to consent in person. A copy of the signed consent form may be mailed or emailed to the participant. The process for consenting when unable to do so in person will include the following:
 - A brief introduction of the study from the treating surgeon.
 - Study staff will be notified of the potential participant from the treating surgeon or their clinic staff.
 - The research staff will attempt to contact the potential participant by phone to introduce the study. An email, text message, or message through MyChart may be sent if the patient does not answer.
 - Once the potential participant is reached by phone, the research team will discuss the study and email, mail, or send the consent form via MyChart if the patient is interested.
 - The patient will be given directions to sign the consent form (either personally or electronically) and email the signed copy back to study staff. Study staff will sign then sign the consent form upon receipt.
 - A copy of the signed consent form will be emailed, mailed, or sent through MyChart to the participant.
 - Study staff will coordinate a day and time to meet with the participant to perform study procedures that are required in person. Any procedures that may be completed remotely can be completed before the scheduled date and time.

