11 REGISTRATION GUIDELINES

Patients must meet all of the eligibility requirements listed in Section 5 prior to registration.

Patients must not have any study procedures or begin protocol treatment prior to registration.

Randomization to the Intervention or Control Arm will be done at the time of enrollment by the enrolling coordinator using OnCore (the Clinical Trials Office’s electronic clinical research management system).

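### One published, fixed block size of 8 in a single-centre trial with no described masking lets staff who tally assignments know about a fifth of allocations in advance

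*Combined protocol and SAP*

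**What the plan says.** Section 10.1 (Randomization) specifies a "uniform 1:1 allocation ratio with block sizes of 8". The plural still names only one size. The section mentions neither random variation of the size nor any limit on who may know it. It adds that "The random allocation sequence will be stratified by the mobility staging (high vs. low) provided by the pre-treatment AM-PAC stage" and by "whether it is a primary or secondary lung cancer diagnosis". Two factors at two levels each give four strata, and both factors must be known before a patient is allocated.

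Four other sections bear on how this works in practice:

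- **Section 3.3:** "This study will open at a single center at the Huntsman Cancer Institute". No site stratum divides the sequence.
- **Section 11:** randomisation "will be done at the time of enrollment by the enrolling coordinator using OnCore".
- **Section 8.1:** Group 1 receives an exercise packet, an activity tracker and physical therapist instruction, which Group 2 does not receive at that visit. No masking of staff is described. The same section says "Enrollment may be postponed, and the decision to do so is dependent on all three principal" investigators' discretion, and lets the pre-surgery visit fall from 1 week to 6 months before surgery, or earlier if needed.
- **Section 4.2.4:** after a high distress score, "ultimately enrollment into the clinical trial will be determined by the enrolling physician".

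**The concern.** An electronic system such as OnCore can hide the list, but it cannot hide what past assignments reveal. In a 1:1 block of known size 8, each arm has four places. Once one arm's four are used, every remaining place in that block belongs to the other arm. One centre, only four strata and visible assignments make a tally feasible.

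Knowing the next allocation matters only if someone can also influence who takes it. Sections 8.1 and 4.2.4 leave some discretion over timing and eligibility. If that discretion followed the expected allocation, the arms could differ in prognosis before treatment starts. The primary ANCOVA in section 10.3 adjusts only for pretreatment six-minute walk (6MW), so it would remove only the part of the difference that baseline distance captures.

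**Working it through.** **Inputs from the plan.** Block size 8, 1:1, four strata (10.1). N = 200, 25% dropout, target difference 39.95 m, SD 100 m, correlation 0.5 (10.2). Two-sided alpha 0.05 (10.3). The plan gives no predictability figure. Its evaluable number reproduces: 200 × (1 − 0.25) = 150, or 75 per arm.

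**Step 1: allocations known with certainty.** A block of 8 has C(8,4) = 70 equally likely orders. Position k is certain when the last m = 9 − k places all belong to one arm, which happens in 2 × C(8 − m, 4) orders.

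| Position | Orders | Probability of certainty |
|---|---|---|
| 1st to 4th | 0/70 | 0% |
| 5th | 2/70 | 2.9% |
| 6th | 10/70 | 14.3% |
| 7th | 30/70 | 42.9% |
| 8th | 70/70 | 100% |

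The sum is 112/70 = 1.6 per block, and 1.6/8 = 20%. Over 25 full blocks that is 40 of 200 allocations.

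**Step 2: incomplete last blocks.** A stratum of 20 has two full blocks and four further places, none of them certain: 2 × 1.6/20 = 16%. A stratum of 50 gives 6 × 1.6/50 = 19.2%. Over the whole trial, an assumed split of 50/50/50/50 or 80/80/20/20 contains 24 full blocks: 24 × 1.6/200 = 19.2%. A split of 100/60/25/15 contains 23 full blocks, and the seven leftover places in the last stratum add 0.029 + 0.143 + 0.429 = 0.6: (36.8 + 0.6)/200 = 18.7%. That is about 37 to 38 patients.

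**Step 3: best-guess accuracy.** Always guessing the arm with more places left is right with probability 0.5, 0.571, 0.571, 0.629, 0.629, 0.714, 0.714 and 1.0 at positions 1 to 8. The sum is 5.329, and 5.329/8 = 66.6%, against 50% by chance.

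**Step 4: illustrative bias if only certain slots are steered.** Assume that the patients placed in those slots differ by D metres in expected 2-month 6MW, beyond what baseline 6MW explains (+D/2 in intervention slots, −D/2 in control slots). The bias is then the fraction certain × D. The standard error from the plan's inputs is 100 × √(1 − 0.5²) × √(2/75) = 14.14 m.

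| Assumed D | Bias at 20% certain | Share of 39.95 m | Bias/SE | Two-sided type I error |
|---|---|---|---|---|
| 20 m | 0.20 × 20 = 4.0 m | 10% | 0.283 | 5.9% |
| 10 m | 0.20 × 10 = 2.0 m | 5% | 0.141 | 5.2% |

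The type I error is P(|Z + bias/SE| > 1.96). D is not in the documents, and the bias is proportional to it.

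**Step 5: effect of varied blocks.** Simulation of 200 patients, unstratified and in the three splits above, assumed a guesser who knows the set of sizes but not the size of each block. With sizes 6, 8 and 10, certain allocations fall to about 1.5-1.8%. Best-guess accuracy stays at about 66%, the same as with fixed blocks of 8. At 2% certain and D = 20 m, the step 4 bias becomes 0.02 × 20 = 0.4 m.

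**The case against.** Several counter-arguments carry weight.

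- **Postponement is a joint decision.** Section 8.1 ties it to all three principal investigators, while the coordinator operates OnCore. The documents do not say that anyone keeps a tally or that the investigators see cumulative assignments by stratum. This lowers the risk but does not remove it.
- **Steering needs a substitute patient.** Sections 3.2 and 3.4 give 200 patients over 33 months plus the COVID-19 extension: at most about 6 a month, or 1.5 per stratum if the strata were equal. A second suitable candidate in the right stratum will often be missing. Even the certain-only scenario is therefore an upper illustration for its assumed D.
- **Other covariates are planned.** The section 10.3 sensitivity analysis adjusts for the list in section 10.2, including age, gender, smoking, neoadjuvant treatment, tumor stage, pain and sleep. That would remove part of any selection effect. It is not the primary analysis, and the list omits comorbidity, motivation and extent of resection.
- **Varied blocks do not stop guessing.** This is correct. Guessing the arm that is behind in the stratum needs no knowledge of block size and works about as well either way.
- **Enrolment status is unknown.** The protocol version is dated November 2021, and few allocations may remain.

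Together these limit the size of the concern and what the remedy can achieve. They leave intact the facts of a single disclosed block size and the certainty that follows from it.

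**Conclusion.** The point holds as an avoidable vulnerability of modest size. About 20% of allocations in full blocks, and 18.7-19.2% across the splits examined, could be known in advance by staff who tally within strata. That figure needs only the block size and visibility of past assignments. Visibility is inferred from the absence of any described masking. The 4 m bias and 5.9% type I error rest on an assumed 20 m difference and on every certain slot being steered; at 10 m they are 2 m and 5.2%.

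Three stronger readings are not supported:

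- **That upcoming allocations in general are predictable.** Only the 8th in a block is always known, the first four never are, and about 80% of allocations are not certain.
- **That selection has occurred.** The documents show discretion, not misuse.
- **That the fix would remove the bias from best-guess steering of every slot.** With ±10 m that bias is (2 × 5.329 − 8)/4 × 10 = 6.6 m, with a type I error of 7.6%. It depends on the 66.6% guess rate, which varied blocks leave almost unchanged, and it needs a suitable substitute at every allocation. It must not be presented as the benefit of the change.

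**What to change.** For any remaining allocations, generate the OnCore lists with randomly varied block sizes (for example 6, 8 and 10) within each of the four strata. Replace the block-size wording in section 10.1 with a statement that allocation is 1:1 in permuted blocks of varying size, and that the sizes are held in a restricted randomisation file unavailable to recruiting staff. Confirm consent, eligibility and both stratum values before the arm is released.

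If few or no allocations remain, report enrolments and postponements by position within block, so that readers can judge whether timing followed predictability.

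The cost is one list change and one edited sentence. Sample size, alpha and power are unchanged. The largest possible imbalance from an unfinished block rises from 4 patients per stratum (half of 8) to 5 (half of 10). Removing the size from the protocol cannot undo past disclosure, but the reduction to about 2% certain already assumes that staff know the set of sizes.

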10.2 Outcomes, Power, and Sample Size Considerations

Objectives and endpoints are described in Section 1. Covariates used in sensitivity or mediation analysis of the objectives will be age, gender, baseline smoking status, primary or secondary lung cancer, neoadjuvant treatment, tumor stage, baseline level of outcome, pain, and sleep.

Power calculations are based on the group effect in an analysis of covariance for the 6MW test at 8 weeks, with baseline 6MW test as covariate. The planned sample size ($n = 200$) allows for a 25% drop out rate (the main reasons for drop outs observed during the pilot study was found to be complications or poor health status preventing follow-up visits as well as distance to study site), leaving at least 150 subjects evaluable for the primary endpoint. The hypothesis is that the difference in the 6MW distance between the study arms (Intervention vs. Control) will be ≥ 39.95 m. This effect size stems from a meta-analysis where 4 weeks of post-surgery exercise training provided a 39.95 increase in the 6MW distance in NSCLC patients.⁸⁷ Consistent with Arbane,¹¹ $SD = 100$ m and correlation = 0.5 between repeated 6MW test measurements on the same subject are assumed. Power to detect the treatment effect was estimated by simulation (in R) of an analysis of covariance model with 6MW test at 2 months postsurgery as outcome, treatment group as primary predictor and pretreatment 6MW test as covariate. Pre and post 6MW test was assumed to be bivariate normally distributed.

10.3 Primary Endpoint Analysis

Analyses will include all patients that are evaluable for our primary endpoint (expected at least $n=150$). The primary outcome will be the group effect for an analysis of covariance model with 6MW test at 2 months post-surgery as outcome and pretreatment 6MW test as covariate, tested at the nominal two-sided 0.05 significance level. A sensitivity analysis will be performed with additional adjustment variables (listed as covariates in Section 10.1). Missing data will be handled using multivariate imputation by chained equations⁸⁸ as implemented in the R package “mice”.

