
Study Product, Dose, Route, Regimen and Duration
	
A personalized exercise regimen based on a patient's AM-PAC score and performed in the outpatient setting starting 2 weeks or more pre-surgery, inpatient for the duration of the hospital stay, and outpatient for approximately 6 months post-surgery.

Statistical Methodology
	
Primary analysis
 
Power calculations are based on the group effect in an analysis of covariance for the 6MW test at 8 weeks, with baseline 6MW test as covariate. The planned sample size (n = 200) allows for a 25% drop out rate leaving at least 150 subjects evaluable for the primary endpoint. The hypothesis is that the difference in the 6MW distance between the study arms (Intervention vs. Control) will be ≥ 39.95 m. This effect size stems from a meta-analysis where 4 weeks of post-surgery exercise training provided a 39.95 increase in the 6MW distance in NSCLC patients. Consistent with Arbane, SD = 100 m and correlation = 0.5 between repeated 6MW test measurements on the same subject are assumed. Power to detect the treatment effect was estimated by simulation (in R) of an analysis of covariance model with 6MW test at 2 months post-surgery as outcome, treatment group as primary predictor and pretreatment 6MW test as covariate. Pre and post 6MW test was assumed to be bivariate normally distributed.
 
Secondary analyses
 
See section 10 for details.

------------------------------------	--

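### The primary ANCOVA leaves out both randomisation strata (AM-PAC stage and primary/secondary cancer); adding them is a free improvement, worth about 0 to 4 points of power if they explain up to 10% of the residual variance

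*Combined protocol and SAP*

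**What the plan says.** Section 10.1 (Randomization) sets 1:1 allocation in blocks of 8, "stratified by the mobility staging (high vs. low) provided by the pre-treatment AM-PAC stage" and also by primary or secondary cancer.

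Section 10.3 (Primary Endpoint Analysis) takes the group effect from an analysis of covariance with "6MW test at 2 months post-surgery as outcome and pretreatment 6MW test as covariate", "tested at the nominal two-sided 0.05 significance level". The power simulation described in Section 10.2 uses the same model.

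Further covariates for the primary endpoint enter only a sensitivity analysis. Section 10.2 lists them as "age, gender, baseline smoking status, primary or secondary lung cancer, neoadjuvant treatment, tumor stage, baseline level of outcome, pain, and sleep". Primary/secondary cancer is on that list and AM-PAC stage is not.

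Sections 10.3 and 10.4 both cite Section 10.1 as the place where the covariates are listed. Section 10.1 names only the two stratification factors; the list is in 10.2.

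**The concern.** Stratified blocks keep the arms balanced on AM-PAC stage and cancer type, so differences between strata contribute little to the error of the treatment contrast. A model without the strata still counts that variation as residual noise. If the strata are prognostic after baseline 6MW, the reported standard error is then larger than the true sampling error. The confidence interval is wider than it need be, the test is conservative, and the trial uses less of its information than the design provides.

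The misdirected cross-reference adds to this. Read literally, it brings both strata into the sensitivity analysis and the Section 10.4 models. Read as the 10.2 list, it leaves AM-PAC stage out of both. On neither reading are the strata in the primary model.

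**Working it through.** **Inputs from the plan.** Effect: "difference in the 6MW distance between the study arms (Intervention vs. Control) will be ≥ 39.95 m". Variability: "SD = 100 m and correlation = 0.5 between repeated 6MW test measurements on the same subject are assumed". Attrition: the sample of 200 "allows for a 25% drop out rate", "leaving at least 150 subjects evaluable for the primary endpoint". Test: two-sided 0.05.

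**Reproducing the plan's figures.**
- Evaluable: 200 × (1 − 0.25) = 150, or 75 per arm.
- Residual SD after baseline 6MW: 100 × √(1 − 0.5²) = 86.60 m.
- SE of the group effect: 86.60 × √(2/75) = 14.14 m.
- Ratio: 39.95 / 14.14 = 2.82. Power is 80.6% by the normal approximation and 80.1% with the noncentral t.
- Sample size for 80% power: 2 × (1.960 + 0.842)² × 86.60² / 39.95² = 73.8, so 74 per arm and 148 in total, against 150 planned.

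Section 10.2 states no power percentage for the primary endpoint, but its inputs imply about 80% for the model without strata.

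**Effect of adding the strata.** Let R² be the share of the 86.60 m residual variance that the two factors explain after baseline 6MW. The documents do not give it, so a range is shown. Residual SD becomes 86.60 × √(1 − R²), and the SE is that value × √(2/75).

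| Assumed R² | Residual SD (m) | SE (m) | Power, strata in model (normal) |
|---|---|---|---|
| 0 | 86.60 | 14.14 | 80.6% |
| 0.02 | 85.73 | 14.00 | 81.4% |
| 0.05 | 84.41 | 13.78 | 82.6% |
| 0.10 | 82.16 | 13.42 | 84.6% |
| 0.20 | 77.46 | 12.65 | 88.5% |

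Noncentral t values are about half a point lower throughout.

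**Simulation check.** 200 randomised in blocks of 8 within four strata, 25% random drop-out, total SD held at 100 m, 4,000 trials per setting. Assumed: 38% high AM-PAC, 30% secondary cancer, and a correlation of 0.5 between the score underlying AM-PAC stage and baseline 6MW. The two true-SE values come from the runs with no effect and with the 39.95 m effect.

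| R² | Model SE, strata omitted (m) | True SE, strata omitted (m) | Type I error, omitted | Power, omitted | Power, included |
|---|---|---|---|---|---|
| 0 | 14.2 | 14.15, 14.31 | 5.00% | 79.32% | 79.25% |
| 0.02 | 14.2 | 14.40, 14.24 | 5.55% | 79.80% | 80.52% |
| 0.05 | 14.2 | 14.13, 13.97 | 4.95% | 80.65% | 81.85% |
| 0.10 | 14.2 | 13.69, 14.07 | 3.57% | 79.78% | 84.00% |
| 0.20 | 14.2 | 13.31, 12.99 | 3.78% | 82.42% | 88.28% |

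Monte Carlo standard errors are about √(0.05 × 0.95 / 4000) = 0.34 points for type I error and √(0.8 × 0.2 / 4000) = 0.63 points for power. The 5.55% is therefore within chance of 5%; the adjusted model gave the same figure in that setting.

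With the strata omitted, the model SE stays near 14.2 m while the true SE falls as the strata become prognostic. Power of the planned model stays at about 80% or slightly above. The gain from including the strata is nil at R² = 0, about 1 point at 0.05 and about 4 points at 0.10.

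**The case against.** The strongest objection is that the benefit may be negligible. AM-PAC stage and 6MW both measure mobility, and baseline 6MW is already in the model, so residual R² could be 0.05 or less. The gain is then at most about 2 points and type I error is near nominal. This stands, and it limits the size of the point. It does not remove the case for adjusting, because the cost is also negligible.

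Two stronger readings are tempting, and the documents support neither.

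*That omitting the strata pulls power below plan, to perhaps 72 to 75%.* Such figures arise only if stratum effects are added on top of a residual SD of 86.6 m. That SD is what remains of the plan's total SD of 100 m after baseline 6MW alone, so any stratum variance is already inside it. Take effects of 60 m (AM-PAC) and 40 m (cancer type), with assumed shares of 40% and 30%. The added variance is 60² × 0.24 + 40² × 0.21 = 1,200, and total SD would be √(10,000 + 1,200) = 106 m. With 80 and 50 m it would be √(10,000 + 2,061) = 110 m. Neither matches the plan's 100 m. With 100 m held, simulated power is 80%, 81% and 83% without the strata for effects of 40/20, 60/40 and 80/50 m, against 82%, 86% and 91% with them. The last case is also extreme: 80 m after baseline adjustment is twice the treatment effect.

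*That AM-PAC stage is used nowhere in the analysis.* If the references to Section 10.1 are taken literally, the Section 10.4 models and the primary sensitivity analysis adjust for both strata. Primary/secondary cancer is covered in those analyses on either reading. The text is ambiguous on AM-PAC there; only its absence from the primary model and from the 10.2 list is certain.

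**Conclusion.** The omission from the primary model is clear from the text. Its consequence is one of efficiency. Where the strata are clearly prognostic (R² of 0.10 to 0.20), type I error falls to about 3.6 to 3.8% and attainable power is forgone. There is no inflation of false positives, and the loss is measured against what the design could deliver, not against the roughly 80% that the plan's inputs imply.

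The size rests on an assumed residual R² and on the assumed stratum shares. This is a free improvement: the direction is secure, the magnitude is not known, and adjusting does no measurable harm if the strata turn out to be uninformative.

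**What to change.** - **Section 10.3:** specify the primary analysis as *ANCOVA of 2-month 6MW on arm, baseline 6MW, AM-PAC stratum (high/low) and primary/secondary cancer, both as randomised*.
- **Imputation:** include both factors in the chained-equations model, so that it contains every term of the analysis model.
- **Cross-references:** change the covariate references to Section 10.1 in Sections 10.3 and 10.4 to Section 10.2, and add AM-PAC stratum to the 10.2 list. The 10.4 models then carry both factors without ambiguity.

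The cost is a short SAP edit and two degrees of freedom out of about 150 observations. Both factors are known at randomisation, so no data collection is added and no patient is lost to missing covariates. The change should be made before unblinded data are analysed.
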